## **INTRODUCTION & BACKGROUND:**

Effective bowel cleansing is paramount for adequate visualization of the colonic mucosa. Inadequate bowel preparation is reported in as high as 20-30 % of all outpatient procedures but it is higher in hospitalized patients with rates up to 50 % being reported. Hospitalization is associated with a risk of poor bowel cleansing and leads to a prolonged length of stay and increased costs in these patients. Improvement in bowel preparation quality of hospitalized patients has shown to decrease the length of stay and save more than \$418,200 annually at a tertiary care hospital.

Patient tolerability of the bowel preparation agent may be an important factor affecting the quality of colon cleansing. Large volume (4-liter) polyethylene glycol electrolyte solution (PEG-ELS) bowel preparation is safe and effective, yet poor patient tolerability secondary to the large volume that needs to be ingested remains it's Achilles' heel. Several, small volume (2-liter) bowel preparation agents are available to counteract this problem. Sodium picosulfate, a stimulant laxative, magnesium oxide, and anhydrous citric acid (SP/MC) preparation is a 10-ounce bowel preparation which has demonstrated comparable efficacy, better tolerability and a lower incidence of adverse events than both 2-liter and 4-liter polyethylene glycol based bowel preparations. In addition to the volume related improvement in tolerability and adverse

events with SP/MC versus other FDA approved bowel preparations, strong evidence shows that ingesting at least half of the bowel preparation on the day of the colonoscopy, called split dosing, rather than a single day before dose administered the evening before the examination, not only maximizes the cleansing efficacy but also improves tolerability as well.

### **IMPACT:**

There are no studies comparing the efficacy and tolerability of small volume versus large volume bowel preparations in hospitalized patients. Furthermore, even though the use of split dosing has demonstrated higher efficacy and improved tolerability in outpatients, there is no literature assessing the impact of split versus single dosing on the quality of bowel preparation in hospitalized patient undergoing colonoscopies. Our study aims to provide data to demonstrate that inpatients experience the same benefit of SP/MC and split dosing as has been noted in outpatients.

### **HYPOTHESIS:**

- 1) SP/MC (sodium picosulfate, magnesium oxide, and anhydrous citric acid) bowel preparation will increase the proportion of inpatients with adequate bowel cleansing compared to 4-liter PEG-ELS bowel preparation. Split dose bowel regimens of 4-liter PEG-ELS and SP/MC will increase the proportion of inpatients with adequate bowel cleansing compared to a single, day before dose of 4-liter PEG-ELS and SP/MC.

### **PRIMARY OUTCOMES:**

The primary end-point of this study will be the percentage of in-patients with “satisfactory” bowel cleansing. The efficacy of bowel cleansing will be measured using the Boston Bowel Preparation Scale (BBPS). The BBPS divides the colon into three segments (right, transverse and left) which are scored from 0 to 3 (0= colonic mucosa not seen due to solid stool that cannot be cleared, 1 = only a portion of mucosa of the colon segment is seen due to staining, residual stool and/or opaque liquid, 2= minor amount of residual staining, small fragments of stool and/or opaque liquid, but mucosa of colon segment is seen well and 3 = entire mucosa of colon segment is seen well with no residual staining, small fragments of stool or opaque liquid).

A total BBPS score  $\geq 6$  AND  $\geq 2$  in all segments of the colon will be defined as a “satisfactory bowel preparation”. BBPS scores of  $< 6$  OR  $< 2$  in any segment of the colon will be taken as “unsatisfactory cleansing in the final analysis”.

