### **SECONDARY OUTCOMES:**

Secondary outcomes that will be measured are 1) tolerability of the bowel preparation assessed by a patient survey using a modified 5-point Likert scale, 2) percentage of patients requiring a repeat procedure due to unsatisfactory bowel preparation, and 3) percentage of patients receiving rescue medications including magnesium citrate or fleets enemas.

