#### **INCLUSION/EXCLUSION CRITERIA:**

All eligible inpatients at Cleveland Clinic older than 18 years of age scheduled for a colonoscopy will be invited to participate in our study. Patients will be excluded if they have/are:

- 1) Creatinine clearance less than 30 ml/min,
- 2) History of heart failure with current shortness of breath at rest causing limited physical activity, arrhythmia, unstable angina ,or acute myocardial infarction,
- 3) Small bowel obstruction, ileus or bowel perforation
- 4) Dementia or cognitive dysfunction to an extent that they cannot perform the study related documentation or consent to participate in the study,
- 5) Gastroparesis,
- 6) Toxic megacolon or undergoing colonoscopy for decompression,
- 7) Taking oral tetracyclines, fluoroquinolones, antibiotics, iron, digoxin, chlorpromazine and penicillamine within 2 hours before or less than 6 hours after administration of CLENPIQ, or stimulant laxatives within 24 hours,
- 8) Allergy to any of the ingredients in CLENPIQ or golytely and/or
- 9) If the procedure is planned in the intensive care unit (ICU).

A member of the study team will identify hospitalized patients who have a colonoscopy procedure scheduled within the next 48 hours. A member of the study team will review the patient's electronic medical record to ensure that the patient is eligible to participate in the study.

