### **ASSESSMENT OF PATIENT TOLERABILITY AND ADVERSE EFFECTS:**

Each patient will be provided a survey at the time of enrollment. The patients will be instructed to complete the survey in “real time” (as they are drinking the preparation). The co-investigator or the study coordinator will collect the survey from the patient prior to receiving sedation for their colonoscopy procedure. The co-investigator or study coordinator will review the survey to ensure all questions are answered.

The purpose of the survey will be to document the following information:

- a. Demographic details (including level of education and annual income),
- b. The start time and end time of the ingestion of bowel cleansing agent,
- c. Total amount of the cleansing agent ingested (to be recorded using a visual depiction of the remaining bowel preparation agent in the container),
- d. Full dose of the bowel cleanser ingested (yes versus no),
- e. Details including the type and timing of symptoms encountered (nausea, vomiting, abdominal pain, bloating, thirst, dizziness, headache or paresthesia),
- f. If any of the above-mentioned symptoms were present prior to the start of the cleansing process, did the use of the purgative agent make them worse (yes versus no),
- g. Ease of use based on a modified 5-point Likert scale: “very easy,” “easy,” “tolerable,” “difficult,” or “very difficult” (score 5–1, respectively),
- h. Palatability based on a modified 5-point Likert scale: “very good,” “good,” “fair,” “bad,” or “worst” (score 5–1, respectively), – *Patients who score ≥3 points in items h) and i) will be classified as the tolerant group.*
- i. Willingness to use the same agent again (yes versus no),

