#### **STATISTICAL ANALYSIS:**

Descriptive data will be presented for all 4 groups; these include means  $\pm$  standard deviations, median [25th, 75th percentiles] or frequency (percent). Regression analysis will be used to assess the primary and secondary outcomes of interest; logistic regression will be used to model satisfactory bowel preparation and need of repeat procedure while proportional odds logistic regression will be used to model tolerability. For each model, the outcome of interest will be modeled as the dependent variable with the type of bowel preparation (PEG-ELS vs. SP/MC) and type of dose (single vs. split) as the independent variables; the interaction between these two will be tested and included in the models if  $p < 0.10$ . SAS (version 9.4, The SAS Institute, Cary, NC) will be used for all analyses and a  $p < 0.05$  will be considered statistically significant.

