#### **VARIABLES TO BE STUDIED:**

- Basic demographics: Age, sex, ethnicity, income status, BMI, educational level.
- Pertinent medical history: Comorbidities including history of diabetes, stroke, Parkinson’s disease, hypertension, thyroid disease, constipation, ASA class, opiate use, TCA use, history of IBD, poor preparation in previous colonoscopies (yes/no), Charleston comorbidity index, use of anti-emetics for the bowel cleansing (yes/no).

- Procedure details: Date, indication, bowel preparation quality (reported as BPPS), type of sedation, start time of the procedure, the end time of the procedure, cecal intubation (yes/no), cecal intubation time and withdrawal time.

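### The plan has no rule for randomised patients without a bowel-preparation score, so the primary comparison could be biased, in either direction, if preparation-related cancellations differ by arm

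*Combined protocol and SAP*

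**What the plan says.** Under Primary Outcomes: "The primary end-point of this study will be the percentage of in-patients with" satisfactory cleansing. Satisfactory means a BBPS total of at least 6 and at least 2 in all segments. A total below 6, or a score below 2 "in any segment of the colon will be taken as" unsatisfactory. The lowest segment score is defined as "0= colonic mucosa not seen due to solid stool that cannot be cleared". Nothing is said about a patient with no score or with a segment that is absent or was not reached.

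Under Statistical Analysis, "logistic regression will be used to model satisfactory bowel preparation and need of repeat procedure", with preparation type and dose type as independent variables. The section names no analysis population, no missing-data method and no sensitivity analysis.

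Under Inclusion/Exclusion Criteria, the study team identifies "hospitalized patients who have a colonoscopy procedure scheduled within the next 48 hours", so randomisation precedes the procedure. Previous colonic resection is not an exclusion.

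Variables to be Studied lists "cecal intubation (yes/no), cecal intubation time and withdrawal time", but neither a cancelled status nor a reason for a missing score. Secondary Outcomes lists the "percentage of patients requiring a repeat procedure due to unsatisfactory bowel preparation" as a separate outcome and does not link it to the primary one.

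**The concern.** A logistic model can use only patients whose outcome is defined. Unless a rule is added, a patient who cannot take the preparation and whose colonoscopy is cancelled is left out of the model, not counted as a failure of the assigned regimen.

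The loss could plausibly depend on arm. The Introduction names poor tolerability of the large volume as the main weakness of 4-litre PEG-ELS and reports better tolerability for SP/MC. Study Design says that patients and physicians are not blinded, so a decision to cancel may be affected by knowledge of the regimen. If more PEG-ELS failures go unscored, PEG-ELS is flattered and a real SP/MC benefit is partly hidden. If more SP/MC failures go unscored, the benefit is inflated.

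A second, smaller problem lies in the scoring rule. The total of at least 6 presupposes three scored segments. With one segment surgically absent, a well-prepared colon can be recorded as unsatisfactory.

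**Working it through.** **1. The plan's own figure.** The Sample Size Calculation section gives 50% on PEG-ELS, a 10-point increase, 95% confidence and 85% power. A two-sided two-proportion test at 0.05 without continuity correction needs 443 per preparation, 886 in total, as stated. At 1000 patients (250 per group, two groups per preparation, so 500 against 500), power is 89.0%. The increase from 886 to 1000 is justified by uncertainty in the assumed rate, not by missing scores.

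The same test stands in below for the preparation term of the logistic model. All unscored shares are assumptions.

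**2. Unscored patients dropped; 50% and 60% taken as true rates among all randomised.** Let p be the true rate, m the unscored share, and every unscored patient a failure. The rate among scored patients is p/(1 − m), and 500 × (1 − m) patients remain per preparation.

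| Unscored, PEG-ELS / SP/MC | Observed PEG-ELS | Observed SP/MC | Difference | Power |
|---|---|---|---|---|
| 10% / 5% | 0.50/0.90 = 55.6% | 0.60/0.95 = 63.2% | 7.6 points | 65% |
| 5% / 10% | 0.50/0.95 = 52.6% | 0.60/0.90 = 66.7% | 14.0 points | 99% |
| 10% / 10% | 0.50/0.90 = 55.6% | 0.60/0.90 = 66.7% | 11.1 points | 93% |
| 5% / 5% | 0.50/0.95 = 52.6% | 0.60/0.95 = 63.2% | 10.5 points | 91% |

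**3. No true difference, 50% in both arms.** With 10% PEG-ELS and 5% SP/MC unscored, the observed rates are 0.50/0.90 = 55.6% and 0.50/0.95 = 52.6%, a false gap of 2.9 points in favour of PEG-ELS. The standard error, with 450 and 475 patients, is about 3.3 points, so the two-sided rejection rate is about 14.5%. With equal loss the gap is zero and the rate stays at 5.0%.

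**4. Milder assumption: half of the unscored would have been satisfactory.** The observed rate is (p − m/2)/(1 − m). With 10% / 5%: PEG-ELS (0.50 − 0.05)/0.90 = 50.0%, SP/MC (0.60 − 0.025)/0.95 = 60.5%, a difference of 10.5 points with power of about 90%. With no true difference, both arms show 50% and the type I error is 5.0%.

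**5. Other base: 50% and 60% hold among scoped patients.** The complete-case analysis then shows the planned 10 points, with power of about 86.5% at 10% / 5%. If the unscored are all failures, the all-randomised rates are 0.50 × 0.90 = 45.0% and 0.60 × 0.95 = 57.0%, a difference of 12.0 points. With 5% / 10% they are 47.5% and 54.0%, a difference of 6.5 points. The planned effect is seen at nearly the planned power, but it is an effect among scoped patients, not among those randomised.

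**6. The scoring rule.** With three scored segments, at least 2 in each gives 2 + 2 + 2 = 6, so the total condition adds nothing. With two segments, 2 + 2 = 4 and 2 + 3 = 5 both fall below 6; only 3 + 3 = 6 passes.

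**The case against.** The strongest reply is that the plan nowhere says unscored patients are excluded. It is silent, and the endpoint is worded as a percentage of inpatients. This is fair as to intent. It does not supply a rule, and the model as written has no outcome to use for such a patient.

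A reader might infer that every aborted procedure is lost. The documents do not support that: a segment hidden by solid stool scores 0, and one segment below 2 already makes the patient unsatisfactory. A postponed colonoscopy may also still yield a score. The gap is mainly cancelled procedures, together with those stopped before segments are scored.

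A reader might also infer that many unscored patients are preparation failures and that the comparison is therefore biased. The documents give neither a cancellation rate nor reasons. Bias in the test of no difference needs the loss, or its reasons, to differ by arm, which is plausible here but not shown.

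The base of the calculation can be challenged too. The 50% derives from 46% among hospitalised patients undergoing colonoscopy, that is, scoped patients. On that base the loss of power shown in step 2 largely disappears. This objection stands as to size: the 65% is an unfavourable case, not an estimate. It does not remove the need for a rule, because step 5 shows that the scoped and all-randomised differences can still part.

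Finally, the total of at least 6 gives some protection against calling a partial examination satisfactory. Any replacement must not let a segment blocked by stool be ignored.

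**Conclusion.** The concern holds as an omission with conditional consequences. The BBPS-only endpoint and the logistic regression, as written, leave out randomised patients with no score, mainly those whose colonoscopy is cancelled. If preparation-related cancellations differ by arm, the primary comparison is biased, and the direction depends on which arm loses more.

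Under the least favourable assumption about the unscored (all failures, with 50% and 60% true among all randomised), an assumed loss of 5% to 10% per arm moves the 10-point difference to between 7.6 and 14.0 points, and unequal loss can raise the type I error to about 14.5%. Equal loss moves the difference by about 1 point and leaves the type I error at 5%. If half of the unscored would have been satisfactory, the distortion is small or absent. If 50% and 60% apply to scoped patients, the planned 10-point difference and nearly all of the planned power are kept, although the all-randomised difference may not be 10 points.

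Separately, the scoring rule records a patient with a surgically absent segment and scores of 2 and 2 as unsatisfactory. The documents do not say how common this is. Both points should be settled before outcomes are seen.

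**What to change.** - Define the primary analysis on all randomised patients in their assigned group.
- Count a colonoscopy not done or not scored because the preparation was not taken, not tolerated or inadequate as unsatisfactory.
- Record the reason for any missing score and report it by arm.
- For scores missing for unrelated reasons, use multiple imputation. Add two sensitivity analyses: complete case, and all missing counted as failure.
- Define satisfactory as at least 2 in every segment anatomically present, and drop the total of at least 6. Score a segment not seen because of stool as 0. Treat a segment not reached for a reason unrelated to preparation as missing.

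The cost is analysis-plan wording, one recorded field, and slightly lower success rates where preparation-related loss occurs. Power should be restated. If 50% and 60% hold among scoped patients, 5% preparation-related loss per arm gives all-randomised rates of 47.5% and 57.0% and power of about 85% at 1000 patients. A 10% loss gives 45.0% and 54.0% and about 81%, and 1106 patients would be needed for 85%.

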### **SAMPLE SIZE CALCULATION:**

Preliminary data has been gathered over the last one year at Cleveland Clinic which has shown adequate bowel preparation rates (as defined by the reported preparation quality of good or excellent on the Aronchik scale) in about 46 % of all hospitalized patients undergoing colonoscopy. Due to the educational initiative currently underway at our institution, we will assume that the rates of adequate bowel preparation will be 50 % (which will be taken as the rate of adequate preparation in our control arm of the 4 L PEG-ELS). To demonstrate a 10 % increase in rates of adequate cleansing with the use of P/MC at a confidence level of 95% and a power of 85 %, a sample size of at least 886 subjects would be required. Counteracting for a possible difference that may exist between our estimated and existing rates of satisfactory bowel preparation, we will increase the sample size by at least 10 % for a total of 1000 patients (250 patients per group).

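### The primary endpoint's fixed total of 6 assumes three scored colon segments, so some patients with a prior colonic resection count as failures although every remaining segment is adequate

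*Combined protocol and SAP*

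**What the plan says.** All references are to the combined protocol and SAP.

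- **PRIMARY OUTCOMES**, scale: "The BBPS divides the colon into three segments (right, transverse and left) which are scored from 0 to 3".
- **PRIMARY OUTCOMES**, success: a total of 6 or more, together with at least 2 "in all segments of the colon will be defined as a “satisfactory bowel preparation".
- **PRIMARY OUTCOMES**, failure: "BBPS scores of $< 6$ OR $< 2$ in any segment of the colon will be taken as “unsatisfactory cleansing in the final analysis". A total under 6 is therefore a failure in its own right.
- **INCLUSION/EXCLUSION CRITERIA**, on who may enter: "All eligible inpatients at Cleveland Clinic older than 18 years of age scheduled for a colonoscopy will be invited to participate in our study". Nine exclusions follow, and none is prior colectomy or segmental resection.
- **VARIABLES TO BE STUDIED**: the history items include "history of IBD, poor preparation in previous colonoscopies (yes/no"), but not prior colonic resection.
- **STATISTICAL ANALYSIS**: "logistic regression will be used to model satisfactory bowel preparation and need of repeat procedure", with preparation type and dose type as the independent variables. There is no term or subset for resection.

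No section says how an absent segment is scored, or whether the threshold changes when fewer than three segments exist.

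**The concern.** A total of 6 is three segments times the minimum adequate score of 2. With one segment removed, the same standard of cleanliness gives 4. The scale's own description of a 2 is that the mucosa can be viewed well despite minor residue, so a patient with 2 in both remaining segments has an adequate preparation by the protocol's terms, yet is a failure by its total.

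The misclassification runs one way, from success to failure. It lowers the reported success percentage, which is the primary endpoint itself, and pulls the difference between agents toward zero. Because resection is not a listed variable, the affected patients could not be identified from the dataset as planned.

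**Working it through.** **Step 1. Which adequate score patterns pass?** List every pattern in which each segment present scores 2 or 3, leaving an absent segment unscored.

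| Segments present | Adequate patterns | Total of 6 or more | Result under the rule |
|---|---|---|---|
| 3 | 8 | 8 | all pass |
| 2 | 4 (2/2, 2/3, 3/2, 3/3) | 1 (3/3) | 2/2, 2/3 and 3/2 fail with totals 4, 5 and 5 |
| 1 | 2 | 0 (maximum 3) | all fail |

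In a fully scored intact colon the total condition adds nothing, since 3 × 2 = 6. If an absent segment is entered as 0, every resected patient fails, including a 3/3, because one segment is then below 2.

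**Step 2. Reproduce the plan's sample size.** Inputs from SAMPLE SIZE CALCULATION: the control assumption that "rates of adequate bowel preparation will be 50" per cent, an increase of 10 points, 95% confidence and 85% power. Sidedness is not stated; two-sided is taken because it reproduces the figure. With p̄ the mean of the two rates and d = p2 − p1:

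n per arm = [1.960 × √(2p̄(1−p̄)) + 1.036 × √(p1(1−p1) + p2(1−p2))]² / d²

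= [1.960 × √0.495 + 1.036 × √0.49]² / 0.01 ≈ 443, or 886 in total. This matches the plan.

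**Step 3. Power at the planned size.** 250 per group and two groups per agent give 500 per agent.

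z = [d√n − 1.960 × √(2p̄(1−p̄))] / √(p1(1−p1) + p2(1−p2)) = (2.236 − 1.379) / 0.700 = 1.224, so power is 89.0%.

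**Step 4. Dilution.** Let r be the share of patients with a resected segment (assumed; not in the documents) and f the fraction of truly adequate resected patients whom the rule fails. If resected patients have the same true success rate as the others and are spread equally over the arms, each observed rate becomes p(1 − r × f).

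- f = 1 is the worst case: all fail.
- f = 0.75 would hold if all had two segments left, the four adequate patterns were equally likely, and the absent segment were left unscored.

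| r (assumed) | Rates, f = 1 | Difference | Power, f = 1 | Total N for 85% power, f = 1 | Power, f = 0.75 |
|---|---|---|---|---|---|
| 0 | 50.0 vs 60.0% | 10.0 | 89.0% | 886 | 89.0% |
| 2% | 49.0 vs 58.8% | 9.8 | 87.6% | 928 | 87.9% |
| 5% | 47.5 vs 57.0% | 9.5 | 85.4% | 990 | 86.3% |
| 10% | 45.0 vs 54.0% | 9.0 | 81.3% | 1106 | 83.4% |

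Example for r = 5%, f = 1: 0.50 × 0.95 = 0.475 and 0.60 × 0.95 = 0.570; z = (2.124 − 1.385) / 0.703 = 1.05, so power is 85.4%.

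These figures are for the simple comparison of agents. The dose contrast was not computed; the same scaling of rates would apply to it.

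**The case against.** Several points on the other side are sound.

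- **Not every clean remnant fails.** A reader might infer that any resected patient with a clean colon is scored a failure. Step 1 shows otherwise: a two-segment 3/3 reaches 6 and passes, and the documents do not say that an absent segment is entered as 0.
- **The total condition is not purely harmful.** A reader might infer that it decides only cases it gets wrong. It can also settle an intact colon with an unscored segment. Cecal intubation is recorded as yes or no, so incomplete examinations are possible, and where poor preparation stopped the examination, calling it a failure is arguably right. A replacement rule must keep that result.
- **The frequency is unknown.** Eligibility follows from the silence of the exclusion list, and no section supports any particular share. At 2% the loss of power is small.
- **The plan has a margin.** It raises 886 to 1000 to allow for error in the assumed rates. That keeps worst-case power at the 85% target for shares up to 5%.
- **Bias between arms is not shown.** The same rule applies to every randomised arm, so a false advantage for one agent is not the expected result. One caution remains: STUDY DESIGN calls the trial assessor-blinded but also says the physician is not blinded, so how an absent segment is entered should not be left to case-by-case choice.
- **The data may be retrievable.** The comorbidity list may not be exhaustive, and data come from the electronic record. Still, no field is planned.
- **The cited scale papers may hold a convention for absent segments.** They are not available here, and the protocol's own sentence classes a total below 6 as unsatisfactory without exception.

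These points limit the size and reach of the problem. They do not remove it: the rule as written gives a wrong classification for identifiable score patterns.

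**Conclusion.** The concern holds in a limited form. Applied literally, the responder rule fails a two-segment colon scored 2/2 or 2/3 and any one-segment colon, although each segment present meets the protocol's own standard. That is a stated rule giving a wrong result, and more than a missing detail.

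The expected consequence is non-differential: slightly lower success rates and a diluted difference. Under the worst case, power goes from about 89% to 87.6%, 85.4% and 81.3% at assumed shares of 2%, 5% and 10%. This rests on 500 per agent, two-sided 5% significance, equal true success in resected and intact patients, and equal spread over the arms. The documents do not support a claim that the trial is underpowered, because only shares above about 5%, which nothing in them establishes, take power below target. The correction is worth making because it is cheap and concerns the primary endpoint.

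**What to change.** In PRIMARY OUTCOMES, drop the total-score condition and define satisfactory preparation as a BBPS of at least 2 in every colon segment anatomically present. State that:

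1. a surgically absent segment is recorded as not applicable, not 0;
2. a segment that is present but not scored, for example because poor preparation prevented reaching it, does not meet the criterion.

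In VARIABLES TO BE STUDIED, add prior colonic resection, with the segments absent.

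The cost is a short change to the endpoint definition and one chart-review field, with no extra patients or procedures. Every fully scored intact colon keeps its present classification. The small downside is that total BBPS is not comparable between resected and intact colons, so any summary of total scores should separate the two.
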